4. SELECTION & WITHDRAWAL OF SUBJECTS

4.1 Patient Selection Criteria

4.1.1 Inclusion criteria

Patients must satisfy all of the following entry criteria before they will be allowed to participate in the study:

- 1. The patient must give written (personally signed and dated) informed consent before starting any study-related procedure, which means any assessment or evaluation that would not have formed part of their normal medical care.
- 2. The patient is male and is 18 years of age or older.
- 3. The patient has a histologically or cytologically confirmed diagnosis of prostate cancer and meets the following criteria:
 - Stage T3 or T4, N (*any*), M (*any*) (see Appendix 1) with a PSA >5ng/ml or
 - Biochemical relapse following radical prostatectomy or radical radiotherapy for prostate cancer
- 4. Medical castration by means of LHRHa therapy is indicated for the patient.
- 5. The patient has a life expectancy of at least 12 months.
- 6. The patient is able and willing to comply with the requirements of the protocol.

4.1.2 Exclusion Criteria

Patients who satisfy any of the following criteria must not be included in the study:

- 1. The patient has undergone bilateral orchidectomy.
- 2. The patient is either scheduled to receive, receiving or anticipated to require any chemotherapy for prostate cancer or any other cancer during the period of his participation in the study.
- 3. The patient is either scheduled to receive, or anticipated to require any surgical intervention for their prostate cancer during the period of his study participation.
- 4. The patient has any condition that in the opinion of the Investigator may preclude the administration of subcutaneous Decapeptyl SR injection.
- 5. The patient has received treatment with any LHRHa within one year prior to study entry.
- 6. The patient has a history of hypersensitivity to Decapeptyl SR or CPA and any of their excipients.
- 7. The patient has any contraindication to treatment with anti-androgens, including, but not limited to clinically significant abnormalities in liver function.

- 8. The patient has been treated with oestrogens or steroid androgens within the 12 months prior to screening, or is receiving treatment with non-steroid antiandrogens at the time of the Screening visit.
- 9. The patient, in the opinion of the Investigator, is at risk of serious complications in the event of tumour flare (e.g. vertebral metastases threatening spinal cord compression, significant obstructive uropathy) on initiation of Decapeptyl SR treatment despite concomitant treatment with anti-androgens.
- 10. The patient has any other condition that, in the opinion of the Investigator, might increase the risk to the patient or decrease the chance of obtaining satisfactory data needed to achieve the objective(s) of the study.
- 11. The patient is likely to require treatment during the study with drugs that are not permitted by the study protocol (See Appendix 2).
- 12. The patient has received any investigational drug therapy within 30 days prior to study entry, or is scheduled to receive such a drug during the study period.
- 13. The patient has a history of, or known current, problems with alcohol abuse.
- 14. The patient has any mental condition rendering him unable to understand the nature, scope and possible consequences of the study.
- 15. The patient has previously been enrolled in the study

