Study Protocol

A Phase II, Open-Label, Single-Arm Study to Assess the Efficacy and Safety of Decapeptyl[®] SR (3 mg and 11.25 mg formulations) when administered by subcutaneous injection.

Short Title: The DISC study

STUDY SU/2006/2424 Protocol Version Number 1.1 20 June 2008 EUDRACT NO: 2006-006595-38

Study Sponsor:

University Hospitals Bristol NHS Foundation Trust R&E Department [name] [contact]

Chief Investigator:

[name] Consultant Urologist Department of Urology Bristol Royal Infirmary [name] [contact] [contact] E-mail: [contact]

Sponsor Contact for SAE Reporting:

Research and Effectiveness Department [name] [contact] [contact]

Ipsen Emergency Contact:

[name] Local Pharmacovigilance Manager [contact] hours) [contact]

PROTOCOL SIGNATURES

Investigator Signature:

I have read and agree to the Final version of the protocol dated 20th April 2007 and entitled: 'A Phase II, Open-Label, Single-Arm Study to Assess the Efficacy and Safety of Decapeptyl[®] SR (3 mg and 11.25 mg formulations) when administered by subcutaneous injection'. I am aware of my responsibilities as an Investigator under the guidelines of Good Clinical Practice (GCP) local regulations and the study protocol. I agree to conduct the study according to these guidelines and to appropriately direct and assist the staff under my control who will be involved in the study.

Investigator Name:	Title:
Signature:	Date:

On behalf of the Sponsor:

Name:	Title:	
Signature	Date:	

SYNOPSIS

Study Title:	Phase II, Open-Label, Single-Arm Study to Assess the Efficacy and Safety of Decapeptyl® SR (3 mg and 11.25 mg formulations) when administered by subcutaneous injection.
Study Objectives:	The purpose of this study is to evaluate the efficacy, safety and tolerability of Decapeptyl [®] SR when administered by subcutaneous (SC) injection.
	For the purpose of this study, patients will be considered to be responders if they achieve a Serum Total Testosterone Castration Level (STTCL), which is defined as a Serum Total Testosterone (STT) level of \leq 50 ng/dL.
	Primary Efficacy Study Objective
	To evaluate the efficacy of Decapeptyl SR when given by SC injection in patients with prostate cancer. This will be determined by evaluating the proportion of patients who achieve STTCL 4 months after the first injection.
	Secondary Study Objectives

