3.5.2 Baseline (Week 0)

Eligible patients will return to the clinic within the following month for the Baseline visit. At the Baseline visit:

- Patients' eligibility for the study will be re-checked.
- Blood samples will be collected for analysis of STT, PSA and plasma triptorelin prior to dosing.
- Any adverse events or changes in concomitant medications since the Screening visit will be recorded.

Patients who are still considered to be eligible for the study after completion of all Baseline assessments will then receive a SC injection of Decapeptyl SR 3 mg. Subcutaneous injections should be administered into the anterior abdominal wall. Details of any immediate injection site reaction(s) will be recorded.

To minimise risk of tumour flare, all patients will start adjuvant therapy with an anti-androgen, cyproterone acetate (CPA). Each patient will take 100 mg CPA, three times a day, for 2 weeks starting on the day of the Baseline visit.

24 hours after the injection, the site will call the patient to check whether there have been any tolerability issues following the injection. Details will be recorded in the patients CRF. Patients will provide feedback on:

- Pain (severity, time of onset in relation to the injection, duration).
- Redness (severity, time of onset in relation to the injection, duration).
- Swelling (severity, time of onset in relation to the injection, duration).
- Severity of injection site reactions will be graded using a 4 point scale (none, mild, moderate and severe).

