8.3 Sample Size Determination

The trial will test the null hypothesis (H0) that the proportion of responders (defined as a subject who achieve STTCL (< 50 ng/dL) 4 months after the first injection is lower or equal to 80% against the alternative hypothesis H1 that the proportion of responders is larger or equal to 95%.

Considering the method developed by A'Hern for exact calculation in single-stage phase II designs, a sample of 42 subjects with a cut-off value fixed at 39 subjects allows the rejection of the null hypothesis with an alpha-risk of 2% (one sided) and an 84% power. A drop out rate of up to 10% is anticipated and to accommodate withdrawals the study sample size has been increased to no more than 50 subjects in total.

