8.3.1 Significance Testing and Estimations

Statistical tests for the primary efficacy criterion will be performed one sided with a type I error rate set at 2.5%.

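### No entry criterion uses the testosterone level measured before treatment, so a man already at or below 50 ng/dL could be enrolled and counted as a responder

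*Protocol*

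**What the plan says.** The synopsis (Study Objectives) states that "patients will be considered to be responders if they achieve a Serum Total Testosterone Castration Level (STTCL"), defined as STT at or below 50 ng/dL. The primary endpoint is the proportion at that level 4 months after the first injection. No condition is placed on the starting value.

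Section 8.3 tests the null hypothesis that this proportion "is lower or equal to 80% against the alternative hypothesis H1 that the proportion of responders is larger or equal to 95"%, using "a sample of 42 subjects with a cut-off value fixed at 39 subjects", with "an alpha-risk of 2% (one sided) and an 84% power". Section 8.3.1 says the primary test is "performed one sided with a type I error rate set at 2.5"%. Sections 8.2 and 8.2.1 place the primary analysis on the ITT population, which is every treated subject.

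On entry:
- Section 4.1.1 admits men with "Biochemical relapse following radical prostatectomy or radical radiotherapy for prostate cancer", as an alternative to T3/T4 disease with raised PSA. It also requires that LHRHa castration be indicated.
- Section 4.1.2 excludes bilateral orchidectomy. It also excludes a man if "The patient has received treatment with any LHRHa within one year prior to study entry", and it excludes certain recent or current hormonal treatments.
- None of the 6 inclusion or 15 exclusion criteria names a testosterone value.

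The measurement exists. Section 3.5.1 and the schedule table include STT at Screening, and section 3.5.2 says "Blood samples will be collected for analysis of STT, PSA and plasma triptorelin prior to dosing". Eligibility is re-checked at that Baseline visit.

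**The concern.** The trial asks whether the subcutaneous route brings testosterone down to the castration level and keeps it there. A man who starts at or below that level carries little information on the question, yet the endpoint scores him as a success if he stays low. The orchidectomy and recent-LHRHa exclusions show that the protocol accepts this principle. They apply it through treatment history, while the direct measure is collected and left out of the criteria.

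The trial has one arm and compares its response rate with a fixed 80%. Any such man who stays low pushes the observed rate upward. The 39-of-42 rule allows only three failures, so small counts matter. The month-1 and month-2 response proportions would be affected in the same way. So would the count of treatment failures in section 8.5 that closes recruitment at 6 or more, because these men would not register as failures.

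**Working it through.** **Inputs from the protocol.** Null rate 0.80, alternative 0.95, n = 42, cut-off 39 (section 8.3); one-sided level 2.5% (section 8.3.1); total recruitment 47 (synopsis, Statistical Methods) or up to 50 (section 8.3).

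**Inputs assumed.** k treated men are at or below 50 ng/dL before the first injection, all k are still so at month 4, and the others respond independently at 80%. The protocol gives no value for k.

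**Step 1: reproduce the plan's figures.** With exact binomial tails, P(X ≥ 39 | n = 42, p = 0.80) = 2.08% and P(X ≥ 39 | n = 42, p = 0.95) = 84.3%. These match the stated 2% and 84%. The synopsis total also reproduces: 42 / 0.9 = 46.7, rounded up to 47.

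**Step 2: add k men who are certain to respond.** The remaining 42 − k must supply 39 − k responders, so

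type I error = P(X ≥ 39 − k | n = 42 − k, p = 0.80),

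expected response rate under the null = [k + 0.80 × (42 − k)] / 42.

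| k | Expected rate under the null | Type I error of 39/42 |
|---|---|---|
| 0 | 80.0% | 2.08% |
| 1 | 80.5% | 2.44% |
| 2 | 81.0% | 2.85% |
| 3 | 81.4% | 3.32% |
| 4 | 81.9% | 3.87% |

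Each such man adds 0.2/42, about 0.5 percentage points, to the expected rate. The 2.5% level is passed at k = 2.

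**Step 3: repeat for the recruitment totals.** Section 8.2.1 analyses all treated men, so the final n may be 47 or 50 rather than 42. The protocol states no cut-off for these sizes. I took the smallest cut-off whose exact tail at 80% does not exceed 2.5%.

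- n = 50, cut-off 46: 1.85% (k=0), 2.14% (k=1), 2.48% (k=2), 2.87% (k=3). The level is passed at k = 3.
- n = 47, cut-off 44: 0.93% (k=0), 1.78% (k=4), 2.44% (k=6), 2.85% (k=7). The level is passed only at k = 7.

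The 47-patient rule tolerates more such men because its exact level starts far below 2.5%.

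**Step 4: check the alternative of scoring such men as failures.** With k = 2 of 42 and a true rate of 95% in the others, the expected observed rate is 0.95 × 40 / 42 = 90.5%. That replaces an upward bias with a downward one.

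**The case against.** The strongest reply is that the gap is narrow. Inclusion criterion 4 requires that LHRHa castration be indicated, which is doubtful for a man known to be castrate. Exclusion 8 removes men given oestrogens or steroid androgens within 12 months, or taking non-steroid anti-androgens at Screening. Exclusion 11 with Appendix 2 removes men likely to need listed drugs, many of them hormonal. Exclusion 10 lets the investigator exclude anyone with a condition that threatens satisfactory data. The LHRHa exclusion covers a full year. This stands, and it is why k should be small. None of these criteria is a testosterone check, however, and two of them rest on judgement. Enrolling a man with low STT would breach no explicit rule, so the data review meeting in section 8.2.1 would have no clear violation to act on.

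A reader might infer that relapsed men typically arrive castrate from earlier LHRHa, so that a large share of the sample is affected. The documents do not support that. The relapse criterion says nothing about earlier LHRHa, and nothing shows how many men had it or that anyone stays castrate beyond a year.

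A reader might also infer that the problem would stay hidden without a control arm. It would not: Baseline STT is measured before dosing, and section 8.4.3 summarises STT at each time-point and its change from baseline.

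Finally, a sensitivity analysis without these men could sit in a statistical analysis plan, so its absence here is no fault. Eligibility, by contrast, belongs in the protocol.

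**Conclusion.** The point holds as a gap in eligibility. STT is measured before treatment, no criterion uses it, and the responder definition ignores the starting value, so a man already at or below 50 ng/dL can be enrolled and counted as a success. If such men enter and stay low, the bias is upward.

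The size is probably modest and cannot be fixed from the documents. It depends on k and on the final n: the 2.5% level is passed with 2 such men of 42, 3 of 50 or 7 of 47. A reader might go further and conclude that the trial's type I error does exceed 2.5%. That does not follow. It needs a count that the protocol does not give, the assumption that low testosterone persists for four months, and a particular sample size and cut-off. The design's own alpha and power are correct as stated. This is a cheap tightening, not an error in the calculation.

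**What to change.** Add one eligibility criterion: screening STT must be above the study's own castration level of 50 ng/dL, with the result available before the Baseline injection. The 2-day to 4-week screening window and the Baseline eligibility re-check leave room for this. Section 6.1.1 names only Baseline and Week 4 for testosterone sampling, so it should be aligned with the schedule table, which includes Screening. The 42 evaluable patients and the cut-off of 39 do not change. The cost is a few screen failures and the need to have the result in hand before Baseline.

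If recruitment has begun, pre-specify that the primary test is run in treated patients with Baseline STT above 50 ng/dL, and report how many were left out. Leave these men out rather than scoring them as non-responders, for the reason in step 4 of the working. The cut-off must then follow the reduced n. With 41 left, 38 responders suffice (type I error 2.44%, power 85.3%). With 40 left, 37 would give 2.85%, so the cut-off becomes 38. There P(X ≥ 38 | n = 40) is 0.79% at a rate of 80% and 67.7% at 95%, the latter being the power. The cost is therefore slightly fewer evaluable patients, with some loss of power if the number falls below 42. Recruiting 47 to 50 gives some cover against that.

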	1. To evaluate the efficacy of an initial treatment with Decapeptyl SR 3 mg when given by SC injection. This will be determined by evaluating the proportion of patients who achieve STTCL 1 month after the first injection.
	2. To evaluate the efficacy of a repeat treatment with Decapeptyl SR 11.25 mg when given by SC injection. This will be determined by evaluating the proportion of patients who achieve STTCL 1 month after the second injection.
	3. To assess the changes in plasma triptorelin levels after administration of Decapeptyl SR by SC injection at all assessment time-points in comparison to Baseline.
	4. To assess changes in the levels of Serum Total Testosterone (STT) and Prostate Specific Antigen (PSA), after administration of Decapeptyl SR via the SC route at all assessment time-points in comparison to Baseline.
	Safety & Tolerability Objectives:
	1. To assess the safety of Decapeptyl SR when administered by SC injection.
	 To assess the tolerability of Decapeptyl SR when administered by SC injection.
Study Design:	This is an open-label, single-arm trial designed to assess the efficacy, safety and tolerability of Decapeptyl SR when administered by SC injection. Enrolled patients will be those who have a diagnosis of prostate cancer and for whom medical castration by means of LHRHa

is indicated. Each patient's participation in the trial will last up 5 months (including Screening period).
During the study, patients will receive one injection of Decapeptyl SR 3 mg (the 1-month sustained release formulation) and one injection of Decapeptyl SR 11.25 mg (the 3-month sustained-release formulation). The 3 mg injection will be administered at the study visit 2, on Day 0 (Baseline) and the 11.25 mg injection will be administered one month later, at visit 3. Patients will have additional follow-up visits at Month 2 and Month 4 (End of Study Visit).
All visit dates will be calculated based on calendar months in order to ensure consistency with the recommended injection schedule for Decapeptyl SR.
Written informed consent will be obtained from all patients prior to any study related procedures or assessments being performed.
All study visits will begin between 09:00 and 11:00 hours as blood samples must be collected during this time window (due to possible diurnal variations in testosterone levels)
Potential patients will be invited to attend a Screening visit (visit 1) for the study. At the Screening visit the following will be collected:

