2.	The patient is either scheduled to receive, receiving, or is anticipated to require any chemotherapy for prostate cancer, or any other cancer, during the period of his participation in the study.
3.	The patient is either scheduled to receive, or anticipated to require any surgical intervention for their prostate cancer during the period of his study participation.
4.	The patient has any condition that in the opinion of the Investigator may preclude the administration of subcutaneous Decapeptyl SR injections.
5.	The patient has received treatment with any LHRHa within 1 year prior to study entry.
6.	The patient has a history of hypersensitivity to Decapeptyl SR or CPA or to any of the excipients of Decapeptyl SR or CPA.
7.	The patient has any contraindication to treatment with anti- androgens, including, but not limited to clinically significant abnormalities in liver function.
8.	The patient has been treated with oestrogens or steroid androgens within the 12 months prior to screening, or is receiving treatment with non-steroid anti-androgens at the time of the Screening visit.
9.	The patient, in the opinion of the Investigator is at risk of serious complications in the event of tumour flare (e.g. vertebral metastases threatening spinal cord compression, significant obstructive

r	
	uropathy) on initiation of Decapeptyl SR treatment, despite concomitant treatment with anti-androgens.
	10. The patient has any other condition that, in the opinion of the Investigator, might increase the risk to the patient or decrease the chance of obtaining satisfactory data needed to achieve the objective(s) of the study.
	11. The patient is likely to require treatment during the study with drugs that are not permitted by the study protocol (For a list of drugs not permitted see Appendix 2).
	12. The patient has received any investigational drug, within 30 days prior to the study or is scheduled to receive such a drug during the study.
	13. The patient has a history of, or known current, problems with alcohol abuse.
	14. The patient has any mental condition rendering him unable to understand the nature, scope and possible consequences of the study.
	15. The patient has previously been enrolled in this study.
Study Treatment:	Study Product: Decapeptyl SR (triptorelin acetate)

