4.2 Patient Withdrawal Criteria

If one or more of the following occurs, the patient will be withdrawn from the study:

- Patient decision to withdraw from the trial.
- Initiation of any oestrogen, any LHRHa (other than the Decapeptyl SR prescribed for this study) or any antiandrogen (other than the cyproterone acetate two week treatment as described in this protocol).
- Unacceptable safety or tolerability as determined by the Investigator.
- Concurrent, non-cancer related reason, which prevents regular follow up of the patient.
- General or specific changes in the patient's condition, which, in the Investigator's judgement, requires medical intervention and prohibits the patient from compliance with the protocol procedures.

If a patient discontinues from the study prematurely (i.e. prior to completion of the protocol), the primary reason for discontinuation will be determined and recorded. In all cases the Investigator will ensure that the patient receives medical follow-up as necessary.

Patients who withdraw from the study will not be replaced. Under no circumstances will patients be enrolled more than once.

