4.3 Contraindications

Hypersensitivity of GnRH analogues or to any of the excipients.

In prostate cancer, DECAPEPTYL SR 3mg should not be prescribed in patients presenting with spinal cord compression or evidence of spinal metastases.

In endometriosis and uterine fibroid treatment, confirm that the patient is not pregnant before beginning treatment.

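### Exclusion 6 is narrower than the hypersensitivity contraindication in both appended SPCs, so a past reaction to another LHRH analogue is left to the investigator's judgement

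*Protocol*

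**What the plan says.** Hypersensitivity is addressed by exclusion criterion 6, which the protocol states twice.

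- Section 4.1.2: "The patient has a history of hypersensitivity to Decapeptyl SR or CPA and any of their excipients".
- Synopsis: "The patient has a history of hypersensitivity to Decapeptyl SR or CPA or to any of the excipients of Decapeptyl SR or CPA".

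Appendix 3 reproduces the SPCs for the 3 mg and 11.25 mg formulations. The contraindications in each open with the same statement: "Hypersensitivity of GnRH analogues or to any of the excipients".

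Earlier treatment with the drug class is addressed by exclusion 5: "The patient has received treatment with any LHRHa within one year prior to study entry". The synopsis, under Study Treatment, describes the regimen as consistent with the SPC. Section 6.3.3 uses the SPC as the reference for whether a reaction is expected.

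**The concern.** The protocol adopts the SPC as its reference for the product, but its specific hypersensitivity criterion covers less than the SPC does. The SPC speaks of a drug class. Among drugs of that class, the criterion names only the study product.

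The neighbouring criteria suggest an oversight. Exclusion 5 is written for the whole LHRH analogue class, and exclusion 7 takes in every contraindication to the anti-androgen. No reason is given for treating the investigational product more narrowly.

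What is at stake is patient safety at entry. A specific criterion on hypersensitivity can lead the person completing the screening form to regard that question as settled. A man with a relevant history could then pass it without the SPC wording being considered.

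**Working it through.** No arithmetic applies, and the protocol states no figure on this point to reproduce. The check is a comparison of texts.

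**Step 1: scope of each statement.**

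| Hypersensitivity to | Exclusion 6, synopsis | Exclusion 6, section 4.1.2 | SPC 3 mg | SPC 11.25 mg |
|---|---|---|---|---|
| Decapeptyl SR | named | named | within the class | within the class |
| Other GnRH/LHRH analogues | not named | not named | contraindicated | contraindicated |
| Excipients of Decapeptyl SR | named, joined by *or* | named, joined by *and* | contraindicated | contraindicated |
| CPA and its excipients | named | named | not addressed | not addressed |

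The substantive difference is in the second row. The third row shows a difference of wording between the two statements of the criterion.

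**Step 2: whether another criterion fills the second row.**

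- Exclusion 5 concerns the timing of earlier LHRH analogue treatment, not reactions to it.
- Exclusion 7 concerns contraindications to anti-androgens only.
- Exclusion 11 and Appendix 2 concern drugs likely to be needed during the study. Leuprorelin and goserelin are listed there as drugs not permitted; a past reaction to them is not mentioned.
- Inclusion 4 requires that LHRH analogue treatment be indicated. It is mandatory but does not mention hypersensitivity.
- Exclusion 4 rests on opinion: "The patient has any condition that in the opinion of the Investigator may preclude the administration of subcutaneous Decapeptyl SR injection".
- Exclusion 10 also rests on opinion: "The patient has any other condition that, in the opinion of the Investigator, might increase the risk to the patient".

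No fixed criterion names a reaction to another analogue. Those that could catch it (inclusion 4, exclusions 4 and 10) call for judgement, and none refers to the SPC contraindications.

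**Step 3: whether such a man could come to screening.** Exclusion 5 looks back one year. A man who received another analogue before that, and reacted to it, is outside its reach. Section 2.3 names leuprorelin as an analogue available in the UK, so earlier exposure to a different analogue is possible.

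**Step 4: how many.** The protocol does not give the share of recruits with earlier LHRH analogue treatment, nor the rate of hypersensitivity to other analogues. The nearest information is section 4.8 of the 11.25 mg SPC, which puts allergic reactions with other marketed triptorelin formulations among the rare reactions. That supports a very small number, but not an estimate.

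**The case against.** The strongest reply is that safeguards exist. A man known to react to LHRH analogues is hard to describe as someone for whom that treatment is indicated, so inclusion 4 should stop him. Exclusions 4 and 10 give the investigator two further grounds, and both SPCs are bound into the protocol. This stands in part: a careful investigator would probably exclude him. It does not remove the mismatch, because the result depends on judgement while the specific criterion is silent.

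It can also be said that exclusion 5 shows only that previously treated men may enter, not that any of them had a reaction. That is correct, and it is why no number is offered.

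Three stronger readings are tempting, and the documents do not support them.

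- A reader might infer that a contraindicated patient would receive a three-month depot that cannot be removed. The protocol says nothing about whether a depot can be removed. The first exposure is the one-month 3 mg form, and "the 11.25 mg injection will be administered one month later, at visit 3". Before that second injection come an injection-site check, a 24-hour call, an adverse-event review and a withdrawal ground: "Unacceptable safety or tolerability as determined by the Investigator". These checks act only after a first exposure, but they mean that the three-month form is not the exposure at issue.
- A reader might infer that a man allergic to another brand of triptorelin would pass. Section 2.2 and the synopsis (Study Treatment) equate Decapeptyl SR with triptorelin, so that example is weak. The gap is clear only for other analogues.
- A reader might infer that a reaction in such a patient would count against the subcutaneous route. Section 6.3.2 assesses causality against the drug and requires alternative causes to be considered, so this is speculation.

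The *and*/*or* difference is mainly editorial. Taken literally, section 4.1.2 could require a reaction to both drug and excipient, but the natural reading is a list.

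**Conclusion.** The point holds as a mismatch within one document: exclusion 6, in both places, is narrower than the contraindication in both SPCs that the protocol appends, and no fixed criterion covers the difference. A past reaction to another LHRH analogue is therefore handled by judgement under inclusion 4 and exclusions 4 and 10.

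The size is probably very small and cannot be quantified from the documents. The primary test, the sample size and the efficacy estimates are untouched. The point merits correction because it concerns safety at entry and costs almost nothing to resolve.

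The conclusion assumes that exclusion 6 is applied as worded, that Decapeptyl SR there means triptorelin, and that the SPCs in Appendix 3 are the product information on which the trial relies. It makes no judgement on which of the two scopes is clinically right.

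**What to change.** Reconcile exclusion 6, in the synopsis and in section 4.1.2, with the hypersensitivity contraindication in the two SPCs of Appendix 3, or add a sentence saying why the protocol departs from it. Use one wording for the excipient clause in both places, and carry the agreed text to the screening form.

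The cost is one line of eligibility wording, repeated where the criterion appears, and at most a rare extra screen failure. Nothing in the statistical section needs to change.
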